- ³ Screening 12-lead ECG, complete blood count (CBC), serum electrolytes, blood urea nitrogen (BUN), creatinine (Cr), glucose, ALT, CPK and urinalysis performed within 45 days prior to first dose administration.
- ⁴ Negative spot urine pregnancy test is required at screening and prior to each study treatment, vulvoscopy and biopsy/surgical excision.
- ⁵ At least 34 mL (4 x 8.5 mL yellow (ACD) tubes) whole blood and 4 mL serum per time point. At least 68 mL whole blood and 8 mL serum should be collected prior to first dose. One additional 8.5 mL yellow (ACD) tube to be collected at Day 0, Week 15 and 48 for microRNA analysis.
- ⁶ At least 51 mL [6 x 8.5 mL yellow (ACD) tubes] whole blood and 4 mL serum should be collected at Week 27.
- ⁷ Cervical colposcopy will be performed once at Day 0, and once at Week 96. For subjects completing the study at Week 78, the repeat cervical colposcopy will be performed at Week 74 or the discharge visit.
- ⁸ HPV genotyping and Pap smears are performed on the same ThinPrep® cervical specimen.
- ⁹ An additional visit may be scheduled to perform vulvoscopy if worsening of disease is suspected. Biopsies should not be performed at any visit other than at entry (Screening), Week 48, Week 74 and Week 96 for subjects in Subgroups C and D prior to Amendment 5.0 unless the Investigator suspects invasive cancer. All biopsy samples and/or excision samples obtained prior to or at the subjects final discharge visit (if not a phone visit) must be sent to the PAC for review.
- ¹⁰ Photography of the acetowhite stained qualifying lesion(s) must be performed prior to and after biopsy, and at all vulvoscopy examinations. If a pre-biopsy digital photograph is not available for a historical biopsy sample at screening, a post biopsy photo will be sufficient. Additionally, standardized high resolution digital photographic imaging should be obtained during examinations of the vagina if lesions are identified, for documentation.
- ¹¹ Tissue specimen from all excised tissue obtained prior to or at the subjects in-person discharge visit must be reviewed by the PAC and will be sent to the central laboratory for HPV testing. All lesions will be biopsied at Week 48, 74, and 96 (as applicable), per Amendment 5.0.
- ¹² HPV genotyping is performed on vulvar tissue specimen using a PCR based assay.

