3. GENERAL STATISTICAL METHODS

3.1. Sample Size Justification

The study will enroll 36 subjects randomized to receive either 6 mg VGX-3100 or 6 mg VGX-3100 plus imiquimod, IM followed by EP in a 2:1 ratio. This sample size provides 80% power to declare each arm superior to historical control with a 1-sided 0.025 type 1 error level for each hypothesis, assuming the true proportion of subjects who achieve the primary endpoint is 20% and 28% for the respective treatment arms and 2% for the historical control, and that 90% of subjects in each treatment group are evaluable at Week 48 from randomization.

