3.7. Multiple Comparisons/Multiplicity

No adjustments for multiple testing will be implemented, as 2 one-sided tests will each utilize a type I error rate of 2.5% on testing the primary hypothesis.

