The number and percentage of subjects with response for the primary endpoint will be presented for each treatment group and compared to historical control separately. A 1-sided p-value and corresponding 2-sided 95% CI using Clopper-Pearson exact binomial methods will be presented for each comparison to prove superiority over historical control. Superiority of VGX-3100 alone or in combination with imiquimod will be declared if 1-sided p-value is <0.025 and the lower end of the CI is greater than 0.02. The primary efficacy will be analyzed separately based on qualifying lesions present at baseline and for all lesions regardless of presence at baseline.

Relevant Output

| Table 14.2.1.1A | Primary Efficacy Analysis: Incidence of Histologic Regression and |
|------------------|-------------------------------------------------------------------|
| | Virologic Clearance at Week 48 (mITT Population) |
| Table 14.2.1.1B | Primary Efficacy Analysis: Incidence of Histologic Regression and |
| | Virologic Clearance at Week 48 (PP Population) |
| Listing 16.2.6.1 | Primary Efficacy Results |

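### The superiority rule is applied to two versions of the primary analysis per arm, qualifying lesions and all lesions, and the SAP never says which one decides

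*SAP*

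**What the plan says.** SAP section 4.3.1 tests each arm against the historical rate with an exact binomial test and a Clopper-Pearson interval. Superiority needs a 1-sided p below 0.025 and a lower limit above 0.02. The section then states: "The primary efficacy will be analyzed separately based on qualifying lesions present at baseline and for all lesions regardless of presence at baseline". Section 4.3.2 defines a qualifying lesion as one confirmed at screening both as HPV-16/18 positive and as HSIL by the pathology committee. It gives that set no priority.

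Section 3.7 says: "No adjustments for multiple testing will be implemented, as 2 one-sided tests will each utilize a type I error rate of 2.5" per cent. Section 3.1 plans the trial "with a 1-sided 0.025 type 1 error level for each hypothesis" and claims: "This sample size provides 80% power to declare each arm superior to historical control". It assumes that "the true proportion of subjects who achieve the primary endpoint is 20% and 28% for the respective treatment arms" and "2% for the historical control", without saying which lesion set these rates describe.

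The responder definition in Table 4-1 names no lesion set. As worded, any vulvar HSIL or any HPV-16/18 in vulvar tissue at evaluation makes the subject a non-responder. Where the SAP wants a ranking it gives one: sections 2.1 and 4.3 make mITT primary and PP supportive. The two lesion sets have no such ranking.

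**The concern.** A superiority rule has to attach to one result. Here it attaches to two results in each arm, so the rule is applied four times in the primary population (2 arms x 2 lesion sets), while section 3.7 describes two tests. If the two versions disagree, nothing in the SAP says whether the arm succeeded. The trial is open-label, so the question would be settled by people who can already see the results. Multifocal disease is a stratification factor (section 1.2.2), so subjects with more than one lesion are expected and disagreement is a practical possibility.

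**Working it through.** **Inputs.** From SAP 3.1: historical rate 0.02, 1-sided level 0.025, assumed rates 0.20 (VGX-3100 alone) and 0.28 (with imiquimod), and "90% of subjects in each treatment group are evaluable at Week 48 from randomization". From SAP 1.2.1: 24 and 12 subjects. From SAP 4.3.1: the superiority rule. Evaluable numbers are 24 x 0.9 = 21.6 and 12 x 0.9 = 10.8, so I use 21 to 22 and 10 to 11.

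**Step 1: reproduce the plan's figure.** For each n, take the smallest r with P(X >= r | n, 0.02) < 0.025. Power is P(X >= r | n, p1).
- VGX-3100 alone, r = 3: power is 79.4% at n=20, 82.1% at n=21 and 84.6% at n=22. So 21 evaluable are needed, and 21/0.9 = 23.3, which rounds up to 24.
- Combination, r = 2: power is 76.6% at n=9, 81.7% at n=10 and 85.8% at n=11. So 10 evaluable are needed, and 10/0.9 = 11.1, which rounds up to 12.

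The total is 36, as stated. The sample size is sound for one test per arm.

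**Step 2: one discordant subject.** This step needs no input beyond the plan's own.

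| Arm | Responders | 1-sided p | Lower limit | Result |
|---|---|---|---|---|
| Combination, n=11 | 2 | 0.0195 | 0.023 | superior |
| Combination, n=11 | 1 | 0.199 | 0.002 | not superior |
| Alone, n=22 | 3 | 0.0093 | 0.029 | superior |
| Alone, n=22 | 2 | 0.071 | 0.011 | not superior |

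For example, P(X >= 1 | 11, 0.02) = 1 - 0.98^11 = 1 - 0.801 = 0.199. Subtracting the probability of exactly one responder, 11 x 0.02 x 0.98^10 = 0.180, gives P(X >= 2) = 0.0195. At these counts, a single subject who responds on qualifying lesions and not on all lesions moves the arm from one verdict to the other.

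**Step 3: type I error.** The exact level per arm is 0.93% (n=22) and 1.95% (n=11). For two tests, 1 - (1 - 0.0093)(1 - 0.0195) = 2.9%. Suppose the sets are nested, meaning that an all-lesion response implies a qualifying-lesion response, with the same subjects in both. Then rejecting on either set is the same event as rejecting on qualifying lesions, and the familywise error stays at 2.9%. Treating all four tests as independent would give 5.6%.

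**Step 4: illustration of power.** Assume that 20% and 28% describe qualifying lesions, and that a fraction d of those responders fail on all lesions. The documents do not give d. All-lesion power is P(X >= r | n, p1(1 - d)).

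| d | Alone, n=21 to 22 | Combination, n=10 to 11 |
|---|---|---|
| 0 | 82.1 to 84.6% | 81.7 to 85.8% |
| 10% | 75.6 to 78.5% | 76.0 to 80.7% |
| 20% | 67.6 to 70.7% | 69.2 to 74.3% |

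Under nesting, the chance that the two analyses disagree is the difference in power. At n=22 and n=11 this is 6.1% and 5.1% for d = 10%, and 13.8% and 11.4% for d = 20%.

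**The case against.** Both analyses are prespecified and both will be reported, in a 36-subject Phase 2 trial. The table shells and the protocol are not at hand and might set an order. This limits the point to one of wording. But the SAP itself introduces the two analyses and states the decision rule, and the rule as written can return two answers.

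A reader might infer that four tests in place of two inflate the type I error towards double. The documents do not support that. Under nesting there is no inflation (step 3).

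A reader might go the other way and take nesting as certain, so that a late choice could only favour the qualifying-lesion version. That is also an inference. Table 4-1 lets the first sample in the window determine histology, so the two versions could rest on different samples. The mITT definition depends on having the endpoint of interest, so the denominators could differ.

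A reader might also infer from footnote 11 to Table 1-1, "All lesions will be biopsied at Week 48, 74, and 96 (as applicable), per Amendment 5.0", that lesions were sampled differently before and after that amendment. The SAP does not show the earlier biopsy rule, the amendment date or how many Week 48 visits came before it, so this cannot be verified and I do not rely on it.

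Finally, it is tempting to recommend the qualifying-lesion set because those lesions are confirmed at screening. That sits badly with Table 4-1, whose wording points to all lesions. The choice is the sponsor's.

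**Conclusion.** The point holds as a defect in the decision rule. Section 4.3.1 leaves the deciding lesion set open, and following the plan exactly can both declare and deny superiority for the same arm. One discordant subject is enough at 2/11 or 3/22 responders; this rests only on the plan's own rates and rule, with 11 and 22 evaluable subjects. The power and disagreement figures in step 4 are illustrations: they depend on assumed discordance of 10% or 20%, on nesting for the disagreement figures, and on the planned rates referring to qualifying lesions. The sample size of 36 is not in error. Because the gap determines whether the primary objective is met, it should be closed before the analysis.

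**What to change.** Before the analysis, make these changes to the SAP.

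- **Section 4.3.1:** name one lesion set, in the mITT population, as the single decision test per arm. Label the other a sensitivity analysis that cannot support a superiority claim. Alternatively, require both versions to pass.
- **Table 4-1:** align the responder definition with that choice. Its present wording points to all lesions, so choosing qualifying lesions would mean restricting it explicitly.
- **Section 3.7:** state that exactly two tests, one per arm, carry the claim. If both versions must pass, state that each arm's claim rests on the joint result.
- **Section 3.1:** state which version the 20% and 28% describe. If they do not describe the deciding version, restate the power for it.

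The cost is a few sentences. No new data are needed, and the sponsor gives up the choice after seeing results.

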4.3.2. Secondary and Exploratory Efficacy Endpoints

Secondary and exploratory efficacy endpoints are supportive to the primary hypothesis.

The following secondary and exploratory efficacy binary endpoints will be presented as percentage point estimates and exact Clopper-Pearson 95% CIs. Each of the following endpoints will be analyzed separately based on qualifying lesions present at baseline and for all lesions regardless of presence at baseline, unless otherwise noted.

- Histologic regression of vulvar HSIL or virologic clearance of HPV-16/18 in vulvar tissue will be assessed at Weeks 74 and 96 by treatment group for all subjects and stratified by subjects who receive 4 or 5 doses (Week 74) and 4, 5, or 6 doses (Week 96).
- Histologic regression of vulvar HSIL will be assessed at Week 48 by treatment group.
- Virologic clearance of HPV-16/18 in vulvar tissue will be assessed at Week 48 by treatment group.
- Histologic regression of vulvar HSIL will be assessed at Weeks 74 and 96 by treatment group for all subjects and stratified by subjects who receive 4 or 5 doses (Week 74) and 4, 5, or 6 doses (Week 96).
- Virologic clearance of HPV-16/18 in vulvar tissue will be assessed at Weeks 74 and 96 by treatment group for all subjects and stratified by subjects who receive 4 or 5 doses (Week 74) and 4, 5, or 6 doses (Week 96).
- Histologic regression of vulvar HSIL to normal tissue will be assessed at Week 48 by treatment group. Normal tissue is defined as having no evidence of vulvar HSIL, no evidence of LSIL (VIN1), and no evidence of condyloma.
- Non-progression of vulvar HSIL to vulvar cancer will be investigated at Week 48 by treatment group. Progression is defined as advancement to carcinoma by histology according to the Pathology Adjudication Committee.
- Virologic clearance of HPV-16/18 outside of the vulva will be assessed at Week 48 by treatment group (for qualifying lesions only) and be presented by anatomic location (cervical, intra anal, oral, and vaginal).
- Histologic regression of vulvar HSIL or virologic clearance of HPV-16/18 in vulvar tissue will be assessed at Weeks 48, 74, and 96 by treatment group.

Reduction in surface area of qualifying vulvar lesion(s) at Weeks 48, 74, and 96 will be assessed by treatment group and determined by quantitative analysis of standardized pre-biopsy photographic imaging. The mean percent change and associated 95% t-distribution based CI will be presented. Also, the percent reduction will be classified as no clinically significant lesion resolution (reduction in lesion area of 0-25%), partial lesion area resolution (>25% and <100% reduction), and complete lesion resolution (no visible lesion). A lesion will be considered qualifying if it is confirmed to be HPV-16 and/or HPV-18 positive and have histologically confirmed vulvar HSIL by the PAC at screening. The percentage of subjects in each lesion category will be summarized by treatment group with point estimates and associated exact Clopper-Pearson 95% CIs.

Regression/clearance endpoints will be summarized with the number and percentage of subjects meeting the endpoint separately by previous vulvoscopy results and by previous HPV test results. The relationship between the regression/clearance endpoints with miRNA profiles will be summarized with the median change from baseline in miRNA profiles by those who achieved versus not achieved the endpoint.

By-subject listings will be provided for all efficacy-related parameters and results.

| Table 14.2.2.1A | Incidence of Histologic Regression at Week 48 (mITT Population) |
|-----------------|--------------------------------------------------------------------------------------------------------|
| Table 14.2.2.1B | Incidence of Histologic Regression at Week 48 (PP Population) |
| Table 14.2.2.2A | Incidence of Vulvar Virologic Clearance at Week 48 (mITT Population) |
| Table 14.2.2.2B | Incidence of Vulvar Virologic Clearance at Week 48 (PP Population) |
| Table 14.2.2.3A | Incidence of Histologic Regression or Virologic Clearance at Week 48 (mITT Population) |
| Table 14.2.2.3B | Incidence of Histologic Regression or Virologic Clearance at Week 48 (PP Population) |
| Table 14.2.2.4A | Incidence of Histologic Regression to Normal at Week 48 (mITT Population) |
| Table 14.2.2.4B | Incidence of Histologic Regression to Normal at Week 48 (PP Population) |
| Table 14.2.2.5A | Incidence of Non-progression to Vulvar Cancer at Week 48 (mITT Population) |
| Table 14.2.2.5B | Incidence of Non-progression to Vulvar Cancer at Week 48 (PP Population) |
| Table 14.2.2.6A | Incidence of Virologic Clearance Outside of the Vulva at Week 48 (mITT Population) |
| Table 14.2.2.6B | Incidence of Virologic Clearance Outside of the Vulva at Week 48 (PP Population) |
| Table 14.2.2.7A | Incidence of Histologic Regression and Virologic Clearance at Week 74 and Week 96 (mITT Population) |
| Table 14.2.2.7B | Incidence of Histologic Regression and Virologic Clearance at Week 74 and Week 96 (PP Population) |
| Table 14.2.2.8A | Incidence of Histologic Regression at Week 74 and Week 96 (mITT Population) |
| Table 14.2.2.8B | Incidence of Histologic Regression at Week 74 and Week 96 (PP Population) |

| Table 14.2.2.9A | Incidence of Vulvar Virologic Clearance at Week 74 and Week 96 (mITT Population) |
|------------------|--------------------------------------------------------------------------------------------------------------------------|
| Table 14.2.2.9B | Incidence of Vulvar Virologic Clearance at Week 74 and Week 96 (PP Population) |
| Table 14.2.2.10A | Incidence of Histologic Regression or Virologic Clearance at Week 48, Week 74, and Week 96 (mITT Population) |
| Table 14.2.2.10B | Incidence of Histologic Regression or Virologic Clearance at Week 48, Week 74, and Week 96 (PP Population) |
| Table 14.2.2.11A | Incidence of Histologic Regression and Virologic Clearance at Week 48 by Previous Vulvoscopy Result (mITT Population) |
| Table 14.2.2.11B | Incidence of Histologic Regression and Virologic Clearance at Week 48 by Previous Vulvoscopy Result (PP Population) |
| Table 14.2.2.12A | Incidence of Histologic Regression and Virologic Clearance at Week 48 by Previous HPV Test Results (mITT Population) |
| Table 14.2.2.12B | Incidence of Histologic Regression and Virologic Clearance at Week 48 by Previous HPV Test Results (PP Population) |
| Table 14.2.2.13A | Incidence of Histologic Regression and Virologic Clearance at Week 48 by Previous miRNA Profile (mITT Population) |
| Table 14.2.2.13B | Incidence of Histologic Regression and Virologic Clearance at Week 48 by Previous miRNA Profile (PP Population) |
| Table 14.2.2.14A | Incidence of Histologic Regression at Week 48 by Previous Vulvoscopy Result (mITT Population) |
| Table 14.2.2.14B | Incidence of Histologic Regression at Week 48 by Previous Vulvoscopy Result (PP Population) |
| Table 14.2.2.15A | Incidence of Histologic Regression at Week 48 by Previous HPV Test Results (mITT Population) |
| Table 14.2.2.15B | Incidence of Histologic Regression at Week 48 by Previous HPV Test Results (PP Population) |
| Table 14.2.2.16A | Incidence of Histologic Regression at Week 48 by Previous miRNA Profile (mITT Population) |
| Table 14.2.2.16B | Incidence of Histologic Regression at Week 48 by Previous miRNA Profile (PP Population) |
| Table 14.2.2.17A | Incidence of Virologic Clearance at Week 48 by Previous Vulvoscopy Result (mITT Population) |
| Table 14.2.2.17B | Incidence of Virologic Clearance at Week 48 by Previous Vulvoscopy Result (PP Population) |
| Table 14.2.2.18A | Incidence of Virologic Clearance at Week 48 by Previous HPV Test Results (mITT Population) |
| Table 14.2.2.18B | Incidence of Virologic Clearance at Week 48 by Previous HPV Test Results (PP Population) |

| Incidence of Virologic Clearance at Week 48 by Previous miRNA Profile (mITT Population) |
|-----------------------------------------------------------------------------------------|
| Incidence of Virologic Clearance at Week 48 by Previous miRNA Profile (PP Population) |
| Change in Surface Area of Qualifying Vulvar Lesion(s) (mITT Population) |
| Change in Surface Area of Qualifying Vulvar Lesion(s) (PP Population) |
| HPV Testing Results: FFPE Vulvar Tissue Samples |
| HPV Testing Results: Cervical ThinPrep and Swab Samples |
| Cervical Colposcopy and Biopsy Results |
| Vulvoscopy and Biopsy Results |
| Photographic Lesion Results |
| miRNA Profiles by Visit |
| |

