- ¹³ Potential dosing, post-treatment assessment, and distribution of the Participant Diary at Week 52 and Week 78 is applicable for partial responders only. Partial responders who reach Week 78 after Amendment 5.0 will not be offered a 6th dose.
- ¹⁴ Subjects will take home imiquimod plus an imiquimod dosing log to document their use of imiquimod. Administration of imiquimod begins on Day 0.
- ¹⁵ A phone call will be used to review the Participant Diary (PD) with subject within 8-14 days following dose 1 and 2. The patient will be expected to bring the PD to the next visit for review.
- ¹⁶ PRO measures (SF-36v2TM, EQ-5D-5L, WOMAN-PRO) plus 2 additional questions will be assessed as described in protocol Section 6.8.

- 1.2.5. Efficacy, Immunology, and Safety Parameters
- 1.2.5.1. Efficacy Parameters

The primary efficacy endpoint is the combined response outcome of histopathologic regression of vulvar HSIL and virologic clearance of HPV-16/18 in vulvar tissue at Week 48.

The secondary efficacy endpoints include the following:

- Histopathological regression is defined as no histologic evidence of vulvar HSIL at Week 48.
- Virologic clearance is defined as no evidence of HPV-16/18 at Week 48 in vulvar tissue samples.
- Proportion of subjects with no histologic evidence of vulvar HSIL or no evidence of HPV-16/18 at Week 48 in vulvar tissue samples (i.e. collected via biopsy or excisional treatment).
- Proportion of subjects with no evidence of vulvar HSIL, no evidence of vulvar LSIL (VIN1), and no evidence of condyloma on histology (i.e. biopsies or excisional treatment) at the Week 48 visit.
- Proportion of subjects with no progression of vulvar HSIL to vulvar cancer from baseline to Week 48 visit.
- Percent reduction in the cumulative surface area of qualifying acetowhite vulvar lesion(s) as determined by the quantitative analysis of standardized pre-biopsy photographic imaging of qualifying lesion(s) at Week 48 compared to baseline. Results will be classified as:
 - No clinically significant lesion resolution (reduction in lesion area of 0-25%),
 - Partial lesion area resolution (>25% and <100% reduction),
 - Complete lesion resolution (no visible lesion).

Exploratory efficacy endpoints include the following:

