4.3.1. Primary Efficacy Endpoint

The primary efficacy endpoint is the combined outcome of histologic regression of vulvar HSIL and virologic clearance of HPV-16/18 at Week 48. Histologic regression is defined as no histologic evidence of vulvar HSIL (normal tissue or vulvar LSIL (VIN 1) or condyloma) at Week 48. Virologic clearance is defined as clearance of HPV 16 or 18 at Week 48. A subject achieves the primary outcome (i.e., is a "responder") if histologic regression and virologic clearance is observed at Week 48 and the subject did not receive any non-study related treatment for vulvar HSIL. A subject is a non-responder if there is histologic evidence of vulvar HSIL or vulvar carcinoma, or evidence of HPV-16/18, or subject received non-study related treatment for vulvar HSIL.

| Table 4-1: | Definition | of Responder | and Non-Responder |
|------------|------------|--------------|-------------------|
|------------|------------|--------------|-------------------|

| Responder | Non-Responder | | |
|-----------------------------------------------------------------------------------------------------------------------------|--------------------------------------------------------------------------------------------------------------|--|--|
| • Subject with no histologic evidence of vulvar HSIL | • Subject with histologic evidence of vulvar HSIL or vulvar carcinoma at evaluation | | |
| AND | OR | | |
| Subject with no evidence of HPV-16 or HPV-18 in vulvar tissue at evaluation AND | Subject with evidence of HPV-16 or HPV-18 in vulvar tissue at evaluation OR | | |
| • Subject did not receive any non-study related treatment for vulvar HSIL | • Subject who received non-study related treatment for vulvar HSIL | | |
| Note: The efficacy time frame is defined by samples obtained any time starting from 14 days prior to the protocol-specified | | | |

target date of Week 48. The first such sample determines the histology endpoint. The most recent HPV clearance result prior to time of the histology sample within the time frame determines the HPV clearance endpoint.

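### Non-study HSIL treatment counts as failure only on the primary endpoint, so a treated subject can still meet the Week 48 vulvar secondary endpoints

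*SAP*

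**What the plan says.** Section 4.3.1 first defines histologic regression and virologic clearance by the Week 48 tissue result. It then adds a separate third condition for a primary responder: no non-study treatment for vulvar HSIL. Table 4-1 gives the mirror image in its non-responder column: "Subject who received non-study related treatment for vulvar HSIL". No start or end of the period is given.

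The secondary endpoints are listed in Section 1.2.5.1 without that condition: "Histopathological regression is defined as no histologic evidence of vulvar HSIL at Week 48". Virologic clearance is defined there in the same way, by the Week 48 tissue result. The analysis text in Section 4.3.2 reads "Histologic regression of vulvar HSIL will be assessed at Week 48 by treatment group" for regression and, for lesion area, "Reduction in surface area of qualifying vulvar lesion(s) at Weeks 48, 74, and 96 will be assessed by treatment group". Neither section refers back to Table 4-1. Section 4.3.2 describes the secondary and exploratory endpoints as supporting the primary hypothesis.

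**The concern.** The primary endpoint is built from regression and clearance, and two of the secondary endpoints are those same components. On the primary, the plan refuses to credit VGX-3100 with a result that follows other treatment. On the components it is silent, so a programmer following the SAP would credit it. One subject could then be a failure on the composite and a success on both of its parts, with no reason given.

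What is at stake is how the supportive rates read. In arms this small, one reclassified subject visibly moves a percentage. If the rule is left open, the choice can also be made after results are known in an open-label trial.

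**Working it through.** **1. The plan's own figure, and the denominators.** The SAP gives no figure for this point. Its sample-size statement supplies the denominators, so I checked that first. Inputs from Section 3.1: "This sample size provides 80% power to declare each arm superior to historical control"; "with a 1-sided 0.025 type 1 error level for each hypothesis"; rates of "20% and 28% for the respective treatment arms and 2% for the historical control"; and "90% of subjects in each treatment group are evaluable at Week 48 from randomization". Section 1.2.1 gives arms of 24 and 12.

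Evaluable numbers: 24 × 0.9 = 21.6 and 12 × 0.9 = 10.8.

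Exact binomial rule: r is the smallest count with P(X ≥ r | n, 0.02) < 0.025, and power is P(X ≥ r | n, p1).

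| Arm | n | r | Actual alpha | Power |
|---|---|---|---|---|
| VGX-3100 alone, p1 = 0.20 | 21 | 3 | 0.0081 | 82.1% |
| VGX-3100 alone, p1 = 0.20 | 22 | 3 | 0.0093 | 84.6% |
| Combination, p1 = 0.28 | 10 | 2 | 0.0162 | 81.7% |
| Combination, p1 = 0.28 | 11 | 2 | 0.0195 | 85.8% |

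Read as at least 80%, the stated power reproduces. I use 22 and 11 below.

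**2. The definitions side by side.**

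| Week 48 endpoint | Judged on | Non-study treatment condition |
|---|---|---|
| Primary composite (4.3.1, Table 4-1) | histology, HPV in tissue, other treatment | yes, no period |
| Histologic regression | histology | none |
| Virologic clearance, vulvar | HPV in tissue | none |
| Regression or clearance | either result | none |
| Regression to normal | histology | none |
| Lesion-area class | photographs | none |

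**3. Does anything else in the SAP close the gap?**
- The mITT set (Section 2.1), which is primary for efficacy, does not remove subjects given other treatment.
- The PP set may remove them as protocol violations, but Section 2.2 leaves that to the sponsor's discretion, and PP is only supportive.
- Section 3.10 on missing data covers only adverse-event and medication dates.
- Table 4-1 cannot be carried over unchanged, because it requires both components and so does not fit a single-component or either-or endpoint.
- The one similar restriction in Section 1.2.5.1 (no surgical intervention) applies to exploratory clearance at non-vulvar sites. Section 4.3.2 does not repeat it.

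**4. Which subjects are affected?** The window in Section 3.11 and the Table 4-1 note opens 14 days before the Week 48 target date. Under that note, the first sample in it decides histology.
- *Treated before the window, sampled, favourable result:* primary non-responder, but meets each vulvar secondary endpoint whose observed result is favourable. This is the gap.
- *Treated before the window, sampled, unfavourable result:* fails both. No discrepancy.
- *Excised inside the window as the first sample:* the excised tissue is itself the deciding sample. If it shows HSIL, there is no regression.
- *Treated, with no Week 48 sample:* lacks the endpoint and is outside mITT for it.

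**5. Size per affected subject.** The shift in a rate is 1/n.
- VGX-3100 alone: 1/22 = 4.5 points (1/21 = 4.8 if rounded down).
- Combination: 1/11 = 9.1 points (1/10 = 10.0 if rounded down).

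Illustration with assumed counts and Clopper-Pearson 95% intervals:
- 4/22 = 18.2% (5.2 to 40.3) becomes 5/22 = 22.7% (7.8 to 45.4).
- 3/11 = 27.3% (6.0 to 61.0) becomes 4/11 = 36.4% (10.9 to 69.2).

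**The case against.** The strongest reply is that reporting the observed Week 48 result regardless of other treatment is a recognised way to describe a component endpoint, and that differing from a composite responder definition is not in itself an error. That stands as a general statement. However, the SAP does not say it intends this, and it presents these endpoints as support for a primary hypothesis that uses the opposite rule.

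There are partial safeguards: the Week 48 analyses are repeated in PP, efficacy results are listed by subject, and concomitant medications and procedures are listed. These would let a reader find such a subject. They would not change the mITT rate.

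Three stronger readings are tempting, and the SAP does not support them.
- *That a treated subject succeeds on every secondary endpoint.* She meets only those whose observed result is favourable. Removing HSIL does not by itself show HPV-16/18 clearance, or absence of LSIL and condyloma. Non-progression adds little, because any subject without carcinoma meets it, treated or not.
- *That the primary rule is limited to treatment before Week 48.* Section 4.3.1 sets no limit, which is itself something to state.
- *That unequal off-study treatment biases a comparison of the arms.* The study is open-label, but no between-arm test is planned. Each arm is tested against the historical control, on the primary endpoint only.

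**Conclusion.** The point holds, confined to the Week 48 vulvar secondary endpoints in the table above. As written, a subject treated off study before the sampling window and then sampled with a favourable result is a primary non-responder who meets those secondary endpoints.

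The primary test and its error rate are unaffected, since the primary already carries the rule. The secondary endpoints are descriptive estimates with intervals. The 4.5 and 9.1 points are the weight of one hypothetical subject, assuming 22 and 11 evaluable. They do not estimate a bias: the SAP gives no count of such subjects, and it could be zero.

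The conclusion rests on the SAP alone. The protocol was not at hand and may hold a rule, but the SAP does not state or cite one for these endpoints. The change is worth making because it is cheap and removes an unexplained inconsistency between a composite and its components.

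**What to change.** - In Section 4.3.2, state that for histologic regression, vulvar virologic clearance, regression or clearance, and regression to normal at Week 48, a subject with non-study vulvar HSIL treatment from Day 0 up to the determining Week 48 sample counts as not meeting the endpoint, consistent with Table 4-1.
- State the same period in Section 4.3.1, and say whether an excision that itself supplies the determining sample falls inside it.
- For lesion area, state that such a subject is not classed as complete resolution and say where she is shown instead. Present the mean percent change also without such subjects, as a sensitivity analysis.
- Exempt non-progression to cancer and non-vulvar virologic clearance. Treatment of a vulvar lesion is no reason to fail a subject on those.
- Keep the observed-result rates as a sensitivity analysis.

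The cost is a few sentences in the SAP and some extra table rows. The treatment flag is already needed for the primary endpoint. Secondary rates may be slightly lower.
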